3. BACKGROUND AND RATIONALE

3.1 Epidemiology of Overweight/Obesity among Cancer Survivors

Obesity is a prevalent and modifiable factor that negatively affects the risk of cancer, and survival from solid tumor cancers.¹¹⁻¹⁴ In the United States, rates of overweight and obesity as measured by Body Mass Index (BMI) have been steadily increasing since the 1960s.¹⁵ In 2011-2012, 68.5% of US adults were obese or overweight (BMI ≥ 25 kg/m²).¹¹ In Maryland, the prevalence of obesity is 27.1%,¹⁶ in Baltimore city, 33.8 % of adults were found to be obese in the 2010 Baltimore City Community Health Survey.¹⁷ Due to the high prevalence of overweight and obesity in the general population, as well as the association between obesity and incidence of many common cancers,¹³ it is likely that obesity and overweight are common among cancer survivors.

There are an estimated 14.5 million cancer survivors living in the United States in 2014,¹⁸ and this number is expected to increase due to improvements in treatment and early detection as well as the aging of the general population.¹⁹ Among male cancer survivors in the US, the most common forms of cancer are prostate (43%), colon & rectum (9%), and melanoma (8%); for female cancer survivors, breast (41%), uterine corpus (8%) and colon & rectum (8%) cancers are most common.¹⁸ In the 2009 Behavioral Risk Factor Surveillance System (BRFSS) study sample, 27.5% of cancer survivors were obese (with significant variation by state), and 31.5 % of cancer survivors had not completed any leisure-time physical activity in the last 30 days.¹⁹

3.2 Evidence of Association between Overweight/Obesity and Cancer

Incidence: In 2007, The International Agency for Research on Cancer (*IARC*) published a comprehensive review of the association between obesity and cancer. This report concluded that there is “convincing” evidence that greater body fatness, most commonly measured by BMI, is a cause of cancers of the esophagus, pancreas, colon and rectum, breast (postmenopause), endometrium, and kidney; and is likely a cause of cancer of the gallbladder.¹² Additionally, the available evidence is “suggestive” of an association of body fatness with liver cancer.¹² Lung cancer is an exception to the general pattern of increased risk of cancer with increasing BMI. *IARC* concludes that despite epidemiological evidence that high BMI is protective of lung cancer, associations are likely due to residual confounding from cigarette smoking or reverse causation stemming from weight loss among those with

undiagnosed lung cancer.¹² A recent study of electronic medical records from the United Kingdom followed over 5 million individuals to evaluate the relationship between average effects of a 5 kg/m² increase in BMI on cancer risk. An elevated risk of incident cancer was found for cancers of the esophagus, colon, rectum, liver, gallbladder, pancreas, postmenopausal breast, cervix, uterus, ovaries, kidney, brain, thyroid, and leukemia.¹³

Survival: In one prospective study of nearly 900,000 men and women in the Cancer Prevention Study II cohort, the risk of death from any cancer was significantly higher among men and women in the highest BMI categories (calculated from self-reported height and weight at study enrollment), compared to normal weight men and women.²⁰ BMI was significantly associated with increased risk of death from cancer of the esophagus, colon and rectum, liver, gallbladder, pancreas, and kidney among men and women. Additionally, among men, greater BMI was associated with death due to stomach and prostate cancer; for women, death from breast, uterine, cervical, and ovarian cancer.²⁰ A pooled analysis from a recent review of 82 studies of breast cancer and survival related to body mass index found that BMI in the obese and overweight range prior to diagnosis of breast cancer was significantly associated with an increased risk of both all-cause mortality and breast cancer mortality, compared to normal weight women.²¹ Additionally, higher BMI measured within a year after diagnosis and one year or later after diagnosis was still associated with all-cause and breast cancer specific mortality.²¹ In a retrospective cohort study of 4376 Swedish men with prostate cancer, obese men had a 47% (HR 1.47, 95% CI 1.03-2.10) higher risk of mortality from any cause compared to men of normal weight, but no significant association was found between BMI and prostate specific mortality or prostate cancer progression.¹⁴ However, men who gained more than 5% of their bodyweight after diagnosis had a significantly increased risk of prostate-specific cancer risk.¹⁴

Recurrence: Among participants in the Nurse's Healthy Study with a diagnosis of breast cancer, BMI prior to diagnosis was positively correlated with recurrence, among never-smokers and post-menopausal women.²² Obesity is also associated with increased risk of prostate cancer recurrence,²³⁻²⁴. Obesity both five years before surgery and 1 year after surgery was associated with an increased risk of recurrence, compared to those of normal weight, in a prospective study of 1337 men who had received a prostatectomy from the same surgeon.²⁴ Thus, it is likely that obesity confers increased risk of cancer recurrence for several types of cancer, and that decreasing rates of obesity might decrease the rates of cancer recurrence in cancer survivors.

3.3 Weight Gain and Weight Loss in Cancer

Weight gain after diagnosis of breast cancer has been well documented. According to a review of studies evaluating weight gain after breast cancer diagnosis, between 50-96% of women diagnosed with early stage breast cancer were found to have gained weight after diagnosis.²⁵ Results from the same review suggest that weight gain is associated with the type of treatment, with women receiving chemotherapy more likely to gain weight than those receiving

surgery and/or radiation.²⁵ Data from the WHEL study demonstrated that only 10% of women returned to their pre-diagnosis weight after six years of follow-up.²⁶ Among survivors of prostate cancer, patterns of weight gain and weight loss are less clear. In a study of Swedish men diagnosed with localized prostate cancer, 14.8% reported a weight gain of more than 5% after diagnosis, but 8.9% experienced a loss of more than 5%, among those still alive after a median of four years after diagnosis.¹⁴ Joshi et al found similar results in a retrospective cohort study of men who had received a prostatectomy: 13.9% of men gained more than 2.2kg and 12.7% of men lost more than 2.2kg between 5 years prior to the surgery and one year after.²⁴

The weight gain that accompanies cancer diagnosis and treatment has been linked to increased recurrence of cancer. Of the 50 studies reviewed by Vance et al, ten evaluated the effect of weight gain after survival on recurrence of cancer.²⁵ Six of these studies found no relationship between weight gain after diagnosis and recurrence of breast cancer, but four of the studies found that weight gain was associated with increased recurrence, including a subsample of the Nurses' Health Study.²⁵ In the study by Joshi et al. mentioned above, the risk of recurrence was twice as high for men who gained more than 2.2kg compared to men for whom weight remained stable.²⁴ Bonn and colleagues also found an almost two-fold increase in the prostate-cancer specific mortality among men who gained more than 5% of their weight at diagnosis, compared to men with stable weight.¹⁴

3.4 Insulin-Like Growth Factor and Adiposity

Insulin-like growth factor I (IGF-1) is a mediator of growth hormone (GH) and is important for cell development and replication. When IGF-1 binds to the insulin-like growth factor I receptor (IGF-1R), pathways for the expression of genes related to cell growth, replication, and apoptosis are activated.²⁷ IGF binding proteins, including the most common, IGFBP-3, regulate IGF by increasing the half-life of IGFs and controlling their ability to bind to receptors.²⁷ IGFBP-3 may also stimulate apoptosis and block cell proliferation through mechanisms independent of IGFs.¹

Several recent observational, cross-sectional studies suggest that IGF-1 has a U-shaped relationship with BMI, with a peak in IGF-1 occurring around a BMI of 25 and then falling at higher BMI levels.²⁸⁻³¹ Another observational study using a racially diverse NHANES sample found that BMI was inversely associated with IGF-1 levels for all sex and race/ethnicity subgroups.³² In obese people, average total IGF-1 is often much lower than total IGF-1 among normal weight people, while free IGF-1 increases as BMI increases.³³

The relationship between weight loss and IGF-1 is unclear. In a small study, 71 obese women were randomized to receive restricted calorie diets or restricted calorie diets plus the weight loss drug Orlistat. Women in the Orlistat group lost more weight and had larger increases in IGF-1 after six months. However, it is unclear if the changes in IGF-1 are a function of the increased weight loss or Orlistat.³⁴ An earlier study of 20 women did not find any change in IGF-I related to weight loss after eight weeks of a low-calorie, low-carbohydrate diet.³⁵ In a recent clinical trial evaluating the effects of diet and exercise interventions on 68 postpartum

women who were overweight or obese prior to pregnancy, neither the diet nor the exercise intervention were associated with significant changes to IGF-I levels, despite weight loss in both intervention groups at both 12 weeks and 1 year.³⁶

A cross-sectional analyses among 700 breast cancer patients indicated higher physical activity levels were associated with lower IGF-I and IGF-3 levels.³⁷ Clinical trials have also demonstrated that exercise programs among breast cancer patients result in lower IGF levels.^{38,39} It was suggested that the strongest association among physical activity and IGF levels among breast cancer patients was associated with higher BMI, lower baseline physical activity levels and the absence of tamoxifen therapy.³⁸ However many of the extant trials have focused on exercise programs that were independent of weight loss efforts. It is not clear if aerobic exercise recommendations associated with a weight loss also result in decreases of IGF levels. Moreover the association among physical activity and IGF appears strongest among breast cancer survivors. No association was found between physical activity and IGF among prostate cancer survivors in three different trials.³⁸

There is some evidence that the type of diet can influence IGF-1 levels. A high-protein diet has been shown to increase IGF-1 among men with prostate cancer,⁴⁰ men with type II diabetes,⁴¹ and among middle-aged non-obese persons.⁴² Reduction in calories, however, has not been noted to lead to decreased IGF-1 levels,^{35,42,43} except when weight loss was substantial.³⁴

Among healthy adults, IGF-1 measurements have been shown to be stable over time.⁴⁴⁻⁴⁷ For example, In a study of over 800 older adults, a correlation of $r=0.94$ was found for IGF-1 levels measured by Immunoradiometric assay 8-54 days apart.⁴⁴ In a study of 1000 Brazilian adults 21-70, IGF-1 levels measured 12 weeks apart had a correlation of $r=0.91$, and the variation between the two measurements was 20% or less in 99% of people.⁴⁷ Regardless of body mass index, IGF-1 and IGFBP-3 were stable throughout a 24-hour observation period in both normal weight and overweight and obese participants.⁴⁸ IGF-1 has also been demonstrated to be stable in cancer patients, both throughout the day⁴⁹ and across several months.⁵⁰⁻⁵²

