16. SAMPLE SIZE

The trial has sufficient resources to enroll ~120 participants, who will be randomly allocated in equal proportions to each of 3 arms:

- Group A: Self-directed weight loss arm.
- Group B: Coach-Directed Behavioral weight loss intervention arm.
- Group C: Pharmacological intervention using metformin.

The primary contrasts are (C vs. A) and (B vs. A). The (C vs. B) contrast is secondary and is not considered in computing power.

The required sample size for the study was powered for testing 2 primary contrasts of change in IGF-1 over time in (1) lifestyle (arm B) vs. self-directed comparison (arm A), and (2) metformin (arm C) vs. self-directed comparison (arm A), each with 80% power and a 2-sided z test with alpha of 0.025. Assuming common SD at baseline and 6-month visit of 60 ng/ml,⁵¹ and a correlation of 0.90 between IGF-1 measures at baseline and 6-month⁴⁷, a total sample of 120 individuals (i.e. N=40 per arm) will allow the detection of a difference of 17.4 ng/ml (~10% reduction) or greater in change of IGF-1 over time between an active intervention arm and the control arm. With 20% random attrition, this trial will still be able to detect a difference

of 19.4 ng/ml or greater in change of IGF-1 over time between an active intervention arm and the control arm.

With the same sample size, the minimal detectable between arm difference in change of IGF1:IGFBP3 ratio over time were evaluated in a similar fashion for (1) arm B vs. A, and (2) arm C vs. A, each with 80% power and a 2-sided alpha of 0.025. Assuming common SD at baseline and 6-month visit of 11 using data available from the POWER trial,⁸¹ and a correlation of 0.80 between IGF-1:IGFBP3 ratio at baseline and 6-month⁴⁷, a total sample of 120 individuals (i.e. N=40 per arm) will allow the detection of a difference of 5.01 (~15% reduction) or greater in the change of IGF-1:IGFBP3 ratio over time between an active intervention arm and the control arm. With 20% random attrition, this trial will still be able to detect a difference of 5.67 or greater in change of IGF-1:IGFBP3 ratio over time between an active intervention arm and the control arm. We will explore the difference in outcome changes over time between arm B and C but this trial is not powered for this test, as the difference between these 2 arms may be small.

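### Section 16 cites a 12-week IGF-1 study in healthy adults for its baseline-to-6-month correlations, so the stated 80% power at the primary endpoint is unsupported and, for IGF-1, may be too favourable.

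*Combined protocol and SAP*

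**What the plan says.** The Introduction sets the primary outcomes as changes in IGF-1 and the IGF-1:IGFBP-3 ratio at 6 months.

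Section 16 powers two contrasts, each active arm against the self-directed arm, "each with 80% power and a 2-sided z test with alpha of 0.025". For IGF-1 the inputs are "Assuming common SD at baseline and 6-month visit of 60 ng/ml" and "a correlation of 0.90 between IGF-1 measures at baseline and 6-month", the latter cited to reference 47. The stated result is a detectable difference of 17.4 ng/ml with 40 per arm. The section adds: "With 20% random attrition, this trial will still be able to detect a difference" of 19.4 ng/ml.

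For the ratio the inputs are an SD of 11 and "a correlation of 0.80 between IGF-1:IGFBP3 ratio at baseline and 6-month", again cited to reference 47. The stated detectable differences are 5.01, and 5.67 with attrition.

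Section 3.4 says what reference 47 is: a study of 1000 Brazilian adults aged 21 to 70 in which "IGF-1 levels measured 12 weeks apart had a correlation of" 0.91. It is cited in a passage on the stability of IGF-1 in healthy adults. Section 3.4 gives no correlation for IGFBP-3 or for the ratio from that study.

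**The concern.** The interval and the population of the cited source do not match the use made of it. Twelve weeks corresponds to this trial's 3-month visit, whose intervention effect section 17.2 places outside the primary and secondary goals. The trial population is cancer survivors under intervention, not healthy adults. The ratio's 0.80 has no described source at all.

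This matters because the detectable difference is proportional to the square root of (1 − r), which changes quickly when r is near 0.9. Sample size is fixed by resources at about 120, so the detection limit is the main thing the power section tells the reader, and a null result would be read against it. The plan shows no sensitivity to r.

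**Working it through.** **Inputs (section 16).** SD 60 ng/ml for IGF-1 and 11 for the ratio, equal at both visits; r = 0.90 and 0.80; n = 40 per arm, or 32 after 20% attrition; two-sided alpha 0.025, z test, 80% power. The sum of the z values is 2.2414 + 0.8416 = 3.0830.

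**Formula.** SD of change = SD × √(2(1 − r)); SE = SD of change × √(2/n); detectable difference = 3.0830 × SE. The change score suits the planned test. Section 17.2 tests the group-by-6-month interaction with baseline as an outcome time point and separate group indicators, which with complete data is essentially a comparison of changes.

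**Step 1: the plan's own IGF-1 figure, r = 0.90.**
- SD of change = 60 × √0.20 = 26.83.
- n = 40: SE = 26.83 × √(2/40) = 6.00; detectable difference = 18.5, against the printed 17.4.
- n = 32: SE = 26.83 × √(2/32) = 6.71; detectable difference = 20.7, against the printed 19.4.
- Power for 17.4 at n = 40: 17.4/6.00 − 2.2414 = 0.659, which gives 74%.

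Baseline adjustment (SD × √(1 − r²)) does not recover the printed pair either: 18.0 and 20.2. Nor does a two-sided alpha of 0.05: 16.8 and 18.8.

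**Step 2: the correlation that the printed figures imply.** 17.4 / (3.0830 × √(2/40)) = 25.24, so r = 1 − 25.24²/(2 × 60²) = 0.912. The figure 19.4 at n = 32 also gives 0.912. At r = 0.91, the 12-week value in section 3.4, the formula gives 17.5 and 19.6. The printed limits are thus close to what the 12-week correlation yields, with no allowance for a longer interval. Whether that is how they arose cannot be told from the document.

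**Step 3: sensitivity for IGF-1.** Correlations below 0.90 are assumptions for illustration.

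| r | n = 40 | n = 32 | Power for 17.4 at n = 40 |
|---|---|---|---|
| 0.91 | 17.5 | 19.6 | 79% |
| 0.90 | 18.5 | 20.7 | 74% |
| 0.85 | 22.7 | 25.3 | 55% |
| 0.80 | 26.2 | 29.2 | 42% |

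**Step 4: the ratio.**
- r = 0.80: SD of change = 11 × √0.40 = 6.96; detectable difference 4.80 (n = 40) and 5.36 (n = 32). The printed 5.01 and 5.67 are larger, so they are conservative against their own inputs; they imply r of about 0.78.
- r = 0.70 (assumption): 11 × √0.60 = 8.52; detectable difference 5.87 and 6.57, above the printed figures.

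**The case against.** Section 16 presents 0.90 as an assumption, and it sits slightly below the cited 0.91. Section 3.4 also says that IGF-1 is stable in cancer patients across several months. Both points are fair, but section 3.4 gives no correlation for those patients, section 16 does not cite those studies for r, and a stable mean level does not establish a within-person correlation of 0.90. The step from 0.91 to 0.90 is not explained, and the printed limits do not reflect even that step.

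The same source also offers evidence the other way. Section 3.4 reports that the two measurements differed by no more than 20% in 99% of people. As a rough check, assume normally distributed changes and a mean of 174 ng/ml (17.4 being called about 10%). Then 20% is about 35 ng/ml and the SD of change is near 35/2.576, about 13.5. Doubling that variance for the longer interval gives about 19, still below the plan's 26.8. This concerns healthy adults at 12 weeks, so it does not establish 0.90 in this trial. It does show that the source does not point only towards a limit that is too favourable.

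A reader might infer that the correlation is shown to decay, because section 3.4 gives 0.94 at 8 to 54 days and 0.91 at 12 weeks, and might project that line to 6 months. The document does not support this. The two values come from different studies, one in over 800 older adults with a named assay and one in Brazilian adults aged 21 to 70 with no assay stated. A correlation depends on the spread between people, so a 0.03 gap across studies is not a decay rate.

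Finally, the primary model estimates its covariance from the trial data, so the validity of the test does not depend on r, and a null result should be read mainly from its confidence interval. That stands, and it limits the consequence to the stated power and detection limit.

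**Conclusion.** The point holds as a lack of support. The document gives no 6-month correlation for either outcome; the cited source is described as a 12-week IGF-1 study in healthy adults, and nothing in section 3.4 supports the ratio's 0.80. The stated 80% power at 17.4 ng/ml (19.4 with attrition) is therefore unsupported at the primary endpoint.

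For IGF-1 the limit may be too favourable. On the plan's own inputs it is already 1.1 ng/ml too low (18.5 − 17.4), or 1.3 with attrition (20.7 − 19.4). If r were 0.80, it would be about 1.5 times the printed value (26.2/17.4).

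Two stronger readings are not supported. One is that the limits are shown to be too favourable because of the interval: a lower 6-month correlation is plausible, but no figure in the document demonstrates it. The other is that all four detectable differences err in that direction: the ratio figures are conservative against their own inputs, and the issue there is only the unsupported correlation. The numbers rest on a common SD at both visits and the change-score z formula.

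**What to change.** In section 16:

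- State that 0.90 and 0.80 are planning assumptions. Say that the IGF-1 value is informed by a 12-week correlation of 0.91 in healthy adults, and do not cite reference 47 for the ratio unless it reports a ratio correlation.
- Replace the IGF-1 figures with 18.5 ng/ml (20.7 with 20% attrition) at r = 0.90, and show sensitivity, for example 22.7 (25.3) at 0.85 and 26.2 (29.2) at 0.80.
- For the ratio, give 4.80 (5.36) at r = 0.80 and 5.87 (6.57) at r = 0.70.
- Label the lower correlations as illustrative. If a 6-month correlation from a comparable population is available, use it and cite it instead.

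The cost is wording. The sample size and the analysis do not change; the only downside is a less favourable stated detection limit for IGF-1.

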3.5 Insulin-like Growth Factor and Cancer Incidence and Recurrence

High levels of circulating IGF-1 have been implicated in the development of cancer.²⁷ High levels of circulating IGF-1 are associated with an increased risk of some common cancers, such as prostate, premenopausal breast, and colorectal; while high levels of circulating IGFBP-3, the main binding protein of IGF-1, is associated with a decreased risk of these cancers.¹ In vitro studies provide evidence that IGF-IR is over expressed on some types of cancer cells and that IGF-IR enhances cell replication and decreases apoptosis.⁵³ In animal models with decreased IGF-1 production, decreased tumorigenesis was seen, while mouse models with high IGF-1 had increased occurrence of cancer.⁵³

In epidemiological studies, there is also evidence that higher levels of IGF-1 are associated with cancer risk. Using data from The European Prospective Investigation into Cancer and

Nutrition (EPIC) study, a prospective study of more than 500,000 Europeans, researchers have found that higher level of IGF-1 increased incidence of prostate cancer⁵⁴, estrogen receptor positive breast cancer,⁵⁵ and thyroid cancer.⁵⁶ High levels of circulating IGF-1 have also been implicated in increased risk of colon and lung cancer.²⁷ Pathways of Metformin on Cancer potentially works on different pathways,⁵⁷ it may augments the effect if various chemotherapy, decreases level of oxidation, decrease production of reactive oxygen species, it may promote weight loss, and most importantly it may decrease the level of insulin-like growth factor 1.

3.6 Metformin and Cancer Risk

Metformin, an oral biguanide antihyperglycemic agent, is the drug most often prescribed to treat type 2 diabetes. The American Diabetes Association Clinical Practice Recommendations 2014 recommend metformin as the first line therapy for type 2 diabetes.⁵⁸ Metformin lowers glucose by inhibiting glucose production in the liver by activating the AMP-activated protein kinase pathway, through a liver kinase BI (LKB1) dependent pathway.^{57,59} Metformin also improves sensitivity to insulin and slows absorption of glucose by the gastrointestinal tract, which lowers glucose levels in the blood.⁵⁷ Several large retrospective studies suggest that individuals with diabetes maintained on metformin vs. other types of diabetic drugs have a lower incidence of several types of cancer, including hepatocellular, pancreatic, and colon cancers³ The mechanism by which metformin might decrease cancer incidence is unknown, and does not appear to be due to glycemic control alone.⁶⁰ Other possible mechanisms include metformin-associated reductions in weight, IGF-1, and other growth factors.

